10.2.1.3. Schedule of Assessments for Subjects Permanently Discontinuing Randomized Treatment

Protocol Activity All assessments pre-dialysis unless otherwise specified	Early Treatment Discontinuation	Day 1 through Week 52 ⁷			
(Note: All visit timings are relative to Day 1)	Visit (within 2 weeks of discontinuing randomized treatment)	Week 4, 16, 28, 40, 52 ± 2 weeks	Unscheduled		
IRT system transaction	Х				
SBP/DBP, HR (pre- and post-dialysis for in-center HD subjects; between treatments for HHD; at study visits per standard of care for PD) (single readings unless otherwise indicated)	X (triplicate)	x	Х		
ECG	Х				
Iron therapy, transfusions ¹	Х	Х	Х		
Serum pregnancy test (FRP only)	Xe				
HemoCue Hgb	Х	Х	Х		
Hematology ³ ,	Х	Х			
Clinical chemistry ³	Х	Х			
Ferritin, total iron, UIBC, hepcidin, lipids, iPTH	Х				
Hospitalization ¹ , kidney transplant ¹	Х	Х	Х		
Non-serious AEs, AEs of special interest, SAEs, clinical events	Х	Х	Х		
Review concomitant medications	Х	Х	Х		
Healthcare resource utilization (subject reported)	Х				
PGI-S, PGI-C ^{4, 9}	Х				
SF-36 ^{4, 9}	Х				
EQ-5D-5L& EQ-VAS ^{4, 5, 9}	Х				
ABPM sub-study (Appendix 12): 24 hour ABPM		X (Week 16)			
Record awake and sleep times		X (Week 16) ²			

Note: see footnotes on next page

200807

Schedule of Assessments for Subjects Permanently Discontinuing Randomized Treatment (Continued)

Protocol activity (visits ± 2 week)		Yea	r 2 7			Yea	r 3 ⁷				Year 47				
(Note: All visit timings are relative to Day 1)	Week 64	Week 76	Week 88	Week 100	Week 112	Week 124	Week 136	Week 148	Week 160	Week 172	Week 184	Week 196	Week 208	Unscheduled	End of Study ⁸
IRT system call															Х
SBP/DBP, HR (pre- and post- dialysis for in-center HD subjects, between treatments for HHD and PD subjects) (single readings unless otherwise indicated)	х	х	х	х	х	х	х	х	х	х	х	х	х	х	Х
HemoCue Hgb	Х	Х	Х	Х	Х	Х	Х	Х	Х	Х	Х	Х	Х	Х	
Hematology ³	Х	Hgb only	Х	Hgb only	Х	Hgb only	Х	Hgb only	Х	Hgb only	Х	Hgb only	Х		Х
Clinical chemistry ³	Х		Х		Х		Х		Х		Х		Х		Х
Hospitalization ¹ , kidney transplant ¹	Х	Х	Х	Х	Х	Х	Х	Х	Х	Х	Х	Х	Х	Х	Х
Non-serious AEs, SAEs, AEs of special interest, clinical events	Х	Х	Х	Х	Х	Х	Х	Х	Х	Х	Х	Х	Х	Х	Х
Review concomitant medications	Х	Х	Х	Х	Х	Х	Х	Х	Х	Х	Х	Х	Х	Х	Х

1. Record in eCRF, if applicable.

2. Subject will record sleep and wake time during the ABPM session.

3. See details on hematology and clinical chemistry in Protocol Section 7.4.11.

4. Only completed at Early Treatment Discontinuation visit if the randomized treatment discontinuation occurs on or before Week 52

5. Only in selected countries. See Protocol Appendix 3.

6. Additional pregnancy test required at subsequent visit. Must be at least 4 weeks after the end of randomized treatment.

7. Phone visits are acceptable in exceptional circumstances.

8. Investigator will inform subject when to attend this End of Study visit.

9. Subjects who are unable to or require assistance to read must not complete the questionnaires.

200807

10.3. Appendix 3: Assessment Windows

Data for continuous variables that are not related to time-to-event will be summarized according to the scheduled visit time period for which they were recorded in the eCRF. Unscheduled assessments will not be slotted to a particular time point, but will remain as unscheduled if they are either summarized or listed unless otherwise specified (i.e. Hgb endpoints described in Section 10.6.3 and BP endpoints described in Section 10.6.4).

200807

10.4. Appendix 4: Treatment States and Phases

10.4.1. Treatment States

Assessments and events will be classified according to time of occurrence relative to the treatment start and stop dates and last non-zero dose date (see Section 10.6.1).

10.4.1.1. Treatment States for Hgb, Iron Parameters, IV Iron Dose Endpoints, Iron Use Summaries, Transfusion and PRO Data

Treatment State	Definition
Pre-Treatment	Date ≤ Treatment Start Date
On-Treatment	Treatment Start Date < Date ≤ Treatment Stop Date + 1 day
Post-Treatment	Date > Treatment Stop Date + 1 day
Post-Randomization	Randomization Date < Date

NOTES:

• If the treatment stop date is missing and the treatment start date is non-missing and Date > Treatment Start Date, then the assessment will be considered to be On-Treatment

10.4.1.2. Treatment States for CV Endpoint Data

Treatment State	Definition
Pre-Treatment	Date < Treatment Start Date
On-Treatment	Treatment Start Date ≤ Date ≤ Last Non-Zero Dose Date + 28 days
Post-Treatment	Date > Last Non-Zero Dose Date + 28 days
Post-Randomization	Randomization Date \leq Date

NOTES:

 If the last non-zero dose date is missing and the treatment start date is non-missing and Date ≥ Treatment Start Date, then the assessment will be considered to be On-Treatment

• Treatment state definitions use the imputed CV endpoint date

10.4.1.3. Treatment States for BP, Lipid Parameters, Clinical Chemistry, Hematology, Other Laboratory Tests, Hepatobiliary (Liver) and Vital Signs Data

Treatment State	Definition
Pre-Treatment	Date ≤ Treatment Start Date
On-Treatment	Treatment Start Date < Date ≤ Last Non-Zero Dose Date + 1 day
Post-Treatment	Date > Last Non-Zero Dose Date + 1 day
Post-Randomization	Randomization Date < Date

NOTES:

• If the last non-zero dose date is missing and the treatment start date is non-missing and Date > treatment start date, then the assessment will be considered to be On-Treatment

10.4.1.4. Treatment States for AE Data

Non-serious AEs and serious AEs are to be recorded on the eCRF starting at the placebo run-in phase. Serious AEs assessed as related to study procedures or related to a GSK concomitant medication are to be recorded on the eCRF from the time a subject consents

200807

to participation in the study. AE of worsening of an on-going event will be counted once in a particular treatment state.

Treatment State	Definition
Pre-treatment	 For subjects with a non-missing screen failure date, if AE onset is on or before the screen failure date: AE Start Date ≤ Screen Failure Date For randomized subjects with a missing treatment start date, all AEs are considered pre-treatment For randomized subjects with a non-missing treatment start date, if AE onset date is before treatment start date: AE Start Date < Treatment Start Date
Placebo Run-In	If AE onset date or AE worsening date is on or after placebo run-in treatment start date & on or before placebo run-in treatment stop date: Placebo Run-in Treatment Start Date \leq AE Start Date \leq Placebo Run-in Treatment Stop Date Placebo Run-in Treatment Start Date \leq AE Worsening Date \leq Placebo Run-in Treatment Stop Date AE worsening during placebo run-in will be defined relative to the maximum intensity of AE prior to placebo run-in start date. AE worsening date is the first date in the placebo run-in period, when AE intensity increased relative to the maximum intensity of the AE prior to placebo run-in start date.
Post- randomization	If AE onset date or AE worsening date is on or after the randomization date Randomization date ≤ AE Start Date Randomization date ≤ AE Worsening Date AE worsening during post-randomization will be defined relative to the maximum intensity of AE prior to randomization date. AE worsening date is the first date in the post-randomization period, when AE intensity
Treatment emergent	increased relative to the maximum intensity of the AE prior to randomization date. If AE onset date or AE worsening date is on or after treatment start date & on or before the last non-zero dose date plus 1 day. Treatment Start Date ≤ AE Start Date ≤ Last Non-Zero Dose Date + 1 day Treatment Start Date ≤ AE Worsening Date ≤ Last Non-Zero Dose Date + 1 day AE worsening during treatment emergent will be defined relative to the maximum intensity of AE prior to randomized treatment start date.
	AE worsening date is the first date in the treatment emergent period, when AE intensity increased relative to the maximum intensity of the AE prior to randomized treatment start date.
Follow-up	If AE onset date or AE worsening date is after the last non-zero dose date plus 1 day. AE Start Date > Last Non-Zero Dose Date + 1 day AE Worsening Date > Last Non-Zero Dose Date + 1 day AE worsening during follow-up will be defined relative to the maximum intensity of AE prior to randomized treatment start date.
Onset /Worsening Time Since 1 st Dose (Days)	AE worsening date is the first date in the follow-up period, when AE intensity increased relative to the maximum intensity of the AE prior to randomized treatment start date. If Treatment Start Date > AE Onset Date = AE Onset Date - Treatment Start Date If Treatment Start Date ≤ AE Onset Date = AE Onset Date - Treatment Start Date +1 If Treatment Start Date > AE Worsening Date = AE Worsening Date - Treatment Start

200807

Treatment State	Definition
	Date If Treatment Start Date ≤ AE Worsening Date = AE Worsening Date - Treatment Start
	Date +1 Missing otherwise.
Onset/Worsening Time Since Last	If Last Non-Zero Dose Date \leq AE onset date: AE onset date – last non-zero dose date +1
Dose (Days)	If Last Non-Zero Dose Date > AE onset date: AE onset date – last non-zero dose date If Last Non-Zero Dose Date ≤ AE worsening date: AE worsening date – last non-zero dose date +1
	If Last Non-Zero Dose Date > AE worsening date: AE worsening date – last non-zero dose date Missing otherwise.
Duration (Days)	AE Resolution Date – AE Onset Date/AE Worsening Date + 1
Drug-related	If relationship is marked 'YES' on eCRF or if the value is missing.

NOTES:

• AEs that occur or worsen during interruptions of randomized study treatment will be classified as treatment emergent and post-randomization.

• If the last non-zero dose date is missing and the treatment start date is non-missing and the AE onset date or AE worsening date is on or after the treatment start date, then the AE will be considered to be treatment emergent.

- If AE onset date or AE worsening date is missing and AE resolution date is before the treatment start date, then
 the AE will be classified as Pre-treatment. If the AE resolution date is after the start of placebo run-in, the AE will
 also be considered a Placebo Run-in AE.

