The number and percentage of subjects reporting treatment emergent AEs leading to discontinuation of randomized treatment will be summarized by treatment group, primary system organ class, and preferred term.

A listing of treatment emergent AEs leading to discontinuation of randomized treatment will be provided.

BP events and BP-related SAEs are defined in Section 10.6.4.

The number and percentage of subjects with at least one on-treatment BP event will be provided for each treatment group. In addition, this summary will include the number and percentage of subjects with at least one on-treatment BP event that is considered clinically significant and the number and percentage of subjects with at least one ontreatment BP event that is considered to be symptomatic.

The number and percentage of subjects reporting at least one treatment emergent BPrelated SAE will be provided for each treatment group. In addition, the number of treatment emergent BP-related SAEs will be summarized by treatment group, primary system organ class, and preferred term.

A listing of other significant adverse events will be produced. Other significant adverse events are events that are not reported as fatal or serious but represent ICH-defined 'Other significant adverse events' (i.e., marked haematological and other laboratory

200807

abnormalities and any adverse events that led to an intervention, including withdrawal of drug treatment, dose reduction, or significant additional concomitant therapy). For this study, other significant AEs will be defined as non-fatal non-serious AEs resulting in an action taken with study treatment of either 'dose interrupted/delayed' or 'dose reduced'.

Other CV Events

GSK has identified other CV events of interest for all clinical studies. In this study, investigators will be required to fill out the specific CV event page of the eCRF for the following CV AEs and SAEs or any event that may potentially be one of the categories listed:

- Arrhythmias
- Pulmonary hypertension
- Valvulopathy
- Revascularization

Electronically generated patient profiles for subjects reporting these events will not be prospectively created.

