10.6. Appendix 6: Derived and Transformed Data

10.6.1. General

Multiple Measurements at One Time Point

- Mean of the measurements will be calculated and used in any derivation of summary statistics but if listed, all data will be presented.
 - Triplicate BP and HR measurements are expected at certain time points (See Section 10.2.1)
- Subjects having both High and Low values for Normal Ranges at any post-baseline visits for safety parameters will be counted in both the High and Low categories of "Any visit post-baseline" row of related summary tables. This will also be applicable to relevant Potential Clinical Importance summary tables.

Randomization Date

• Date subject was randomized

Treatment Start Date

• First randomized treatment dose start date

Last Non-Zero Dose Date

- Date of last actual dose of randomized study treatment from the IP Discontinuation eCRF form.
 - The dose steps used by the dosing algorithm described in the protocol include a dose hold or a zero dose. If subjects are assigned by the algorithm to a zero dose, they do not receive randomized treatment for that period. Hence, it would be possible for a subject to complete the study, while still following the dosing algorithm, but not be actually taking any actual randomized treatment. The last non-zero dose date, then captures the latest date in the study that a subject physically took a dose of randomized treatment.
- The eCRF allows for the possibility of partial or missing dates to be recorded for the last actual dose of randomized study treatment on the IP Discontinuation form (i.e., missing day, or day and month, or day and month and year). In such a case, or in case of subjects who have a non-missing treatment start date, but are a missing an IP Discontinuation form, the following conventions will be applied in order to impute a last non-zero dose date:
 - Missing day:
 - The last day of the month will be used, unless the treatment stop date also occurs in the same month; in this case, the treatment stop date will be used.
 - Missing day and month;
 - '31' will be used for the day and 'Dec' will be used for the month, unless the treatment stop date also occurs in the same year; in this case the treatment stop date will be used.
 - Missing day, month, and year:
 - Treatment stop date will be used only for subjects who have a nonmissing treatment start date.

200807

Treatment Stop Date				

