10.6.3.6. Dose Adjustment Scheme Endpoints

Dose Adjustment S	cheme Endpoints		
General			
•	assigns all randomized me specified in the pro	d treatment doses in accord otocol.	ance with the dose
• •	 it is possible for subjection unscheduled visits. 	ects to change randomized t	reatment doses at both
• Sites are instructed to complete an exposure record every time dosing instruction is received from the IRT, with the exception of re-dispensing situations where the subject is instructed to continue using the same randomized treatment.			
• Summary tables for some dose adjustment scheme endpoints may summarize subjects by the type of rhEPO treatment received (i.e., epoetin alfa, darbepoetin alfa). Since it is possible for subjects to switch from epoetin alfa to darbepoetin alfa during the study, these displays will include subjects who switch rhEPO treatments in both the epoetin alfa and darbepoetin alfa groups.			
Daprodustat Doses			
Sites will enter the dose of daprodustat into exposure records – the daily frequency will be auto- populated for this randomized treatment. The dose steps of daprodustat are shown below:			
	Total Daily Dose	How Administered	

200807

Dose A	djustment Scheme Endpoi	nts
	1 mg	single 1 mg tablet
	2 mg	single 2 mg tablet
4 mg		single 4 mg tablet
6 mg		single 6 mg tablet
	8 mg	single 8 mg tablet
	10 mg	single 10 mg tablet
	12 mg	two 6 mg tablets
	16 mg	two 8 mg tablets
	24 mg	three 8 mg tablets
Epoetin	Alfa Doses	
dose ste	eps of epoetin alfa (including	cy of each dose of epoetin alfa into exposure records. The the corresponding total weekly doses) are shown below:
	Total Weekly Dose	Dose and Frequency
	1500	1500 U once a week
	2000	2000 U once a week
	3000	3000 U once a week
	4000	4000 U once a week
	5000	5000 U once a week
	6000	6000 U once a week
	8000	8000 U once a week
	10000	10000 U once a week
	12000	4000 U 3 times a week
	15000	5000 U 3 times a week
	18000	6000 U 3 times a week
	21000	7000 U 3 times a week
	24000	8000 U 3 times a week
	27000	9000 U 3 times a week
	30000	10000 U 3 times a week
	36000	12000 U 3 times a week
	42000	14000 U 3 times a week
	48000	16000 U 3 times a week
	60000	20000 U 3 times a week
	oetin Alfa Doses	
	•	cy of each dose of darbepoetin alfa into exposure records. Including the corresponding total 4-weekly doses) are shown
Ŀ	Total 4-Weekly Dose	Pre-filled Syringe Dose and Frequency
L		

Dose Adjustment Scheme	Endpoints			
30 µg	30 µg every 4 weeks			
40 µg	40 µg every 4 weeks			

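### The treatment-emergent AE window closes one day after the last physical dose in both arms, so AEs that end treatment between doses are counted on daily daprodustat but often missed on rhEPO

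*SAP*

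**What the plan says.** **AE window.** Under section 10.4.1.4 an AE is treatment emergent if its onset or worsening falls between treatment start and a date "on or before the last non-zero dose date plus 1 day". Anything later is follow-up. AEs during interruptions of randomized treatment still count as treatment emergent.

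**Anchor.** Section 10.6.1 says that the last non-zero dose date "captures the latest date in the study that a subject physically took a dose of randomized treatment". It marks the last dose taken, not the end of the period which that dose was meant to cover.

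**Other windows.** Cardiovascular endpoints are on-treatment when "Treatment Start Date ≤ Date ≤ Last Non-Zero Dose Date + 28 days" (section 10.4.1.2). BP, laboratory and vital-sign data use "Treatment Start Date < Date ≤ Last Non-Zero Dose Date + 1 day" (section 10.4.1.3). No window varies by arm or dosing frequency.

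**Dosing frequencies.** In section 10.6.3.6 daprodustat is daily. Epoetin alfa steps run up to "10000 U once a week" and are three times weekly above that. Darbepoetin alfa is given every 4, 2 or 1 weeks. Section 10.14.1.3 assigns epoetin to HD subjects and darbepoetin to PD subjects.

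**Uses.** The AE window feeds the Tier 1 and Tier 2 between-arm tests (section 8.2.4) and the SAE and fatal SAE tables (section 8.2.4.2). The same section says that subjects reporting "treatment emergent AEs leading to discontinuation of randomized treatment will be summarized". The 28-day window feeds the supportive while on-treatment CV analyses (sections 7.2.2 and 8.2.1.2).

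**The concern.** One day after a dose spans a whole daprodustat interval but only the start of a weekly or longer rhEPO interval. Take a subject on weekly epoetin whose AE begins on day 3 after a dose. If another dose follows, the AE is treatment emergent. If the AE makes the subject stop, or kills the subject before the next dose, the same AE becomes follow-up. The classification depends on what happens afterwards, and with on-schedule dosing this can happen only in the comparator arm.

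Elsewhere the SAP accepts that a dose covers its interval. It extends medication records by gap factors: 6 days for weekly and 13 days for two-weekly prior ESA (section 10.6.2.2), and 27 days for four-weekly IV iron (section 10.6.3.2). It makes no such allowance for randomized rhEPO.

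At stake is a false imbalance against daprodustat in the safety tables. It would be worst in the table meant to count AEs that cause stopping, and it could produce spurious Tier 1 or Tier 2 signals. A post-randomization AE state is defined in section 10.4.1.4, but sections 8.2.4 and 8.2.4.2 describe no between-arm AE display that uses it and no window adjusted for dosing interval.

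**Working it through.** The SAP states no figure that depends on these windows, so there is none to reproduce. The check counts days.

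**Inputs.** Windows of +1 day (10.4.1.4) and +28 days (10.4.1.2); regimens from 10.6.3.6.

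**Assumptions.** Dosing is on schedule, an event is equally likely on any day of the cycle, and the event ends treatment before the next dose. Three-times-weekly dosing is placed on days 0, 2 and 4 of a 7-day cycle.

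**Step 1: AE window.** Let the lag be the days since the last dose. The event is counted if lag ≤ 1, so capture = (days in the cycle with lag 0 or 1) / (cycle length).

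**Step 2: CV window.** The event is counted if lag ≤ 28. The tail left after the event is 28 − lag.

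| Regimen | AE capture | Mean (max) days already past the +1 day limit | CV tail, mean (min) days |
|---|---|---|---|
| Daprodustat daily | 1/1 = 100% | 0 (0) | 28.0 (28) |
| Epoetin three times weekly | 6/7 = 86% | 0.1 (1) | 27.3 (26) |
| Weekly | 2/7 = 29% | 2.1 (5) | 25.0 (22) |
| Every 2 weeks | 2/14 = 14% | 5.6 (12) | 21.5 (15) |
| Every 4 weeks | 2/28 = 7% | 12.5 (26) | 14.5 (1) |

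The longest lag is 27 days (every 4 weeks), so the 28-day CV window captures such an event in every regimen. Only the tail differs.

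**Step 3: effect on an all-AE relative risk.** Let s be the share of AE subjects whose event comes at stopping, and c the capture from Step 1. With equal true risk, daprodustat keeps all its events and rhEPO keeps (1 − s) + s·c of its events. The observed relative risk (daprodustat/rhEPO) is 1 / [(1 − s) + s·c].

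| s (assumed) | All three times weekly, c = 6/7 | All weekly, c = 2/7 | All every 4 weeks, c = 2/28 |
|---|---|---|---|
| 10% | 1.01 | 1.08 | 1.10 |
| 20% | 1.03 | 1.17 | 1.23 |
| 40% | 1.06 | 1.40 | 1.59 |

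Example: s = 0.4, weekly: 1 / (0.6 + 0.4 × 2/7) = 1 / 0.714 = 1.40.

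The SAP gives neither s nor the regimen mix, so these values are a range and not an estimate.

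**The case against.** **Only the final interval is exposed.** Every AE that starts before the last dose counts whatever the regimen, as do AEs during interruptions. This stands, and it is why Step 3 dilutes the effect by s. A reader might go further and assume, say, 60% weekly, 30% three times weekly and 10% four-weekly dosing. The loss is then 0.6 × 0.714 + 0.3 × 0.143 + 0.1 × 0.929 = 56%, so a true 5% in each arm would show as 5% against 2.2%, a relative risk near 2.3. The documents do not support that as a statement about the AE tables. It applies only to events that end treatment, and the SAP has no such mix.

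**Rates are partly protected.** Section 10.6.4.3 censors treatment-emergent person-time at the last non-zero dose, or one day after it, and the Tier 1 and Tier 2 tables report rates per 100 person-years. This stands in part. It does not protect counts, percentages, the Cochran-Mantel-Haenszel tests or relative risks. Rates are still distorted if events cluster at stopping.

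**The CV window is not faulty in the same way.** This stands. A reader might infer that on-treatment MACE loses stopping events as AEs do; it does not when dosing is on schedule. The co-primary and principal secondary CV analyses follow subjects to study completion or withdrawal (section 10.6.4.1) and do not use this window.

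**BP, laboratory and vital signs.** A reader might carry the AE result over to these, since they share the +1 day rule. They are measured at visits, and the early discontinuation visit may fall up to 2 weeks after stopping (section 10.2.1.3), so daprodustat values can also be lost. No difference between the arms has been shown.

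**Other displays help.** Reasons for stopping treatment and all-cause mortality are reported in the ITT population without the +1 day limit. Deaths and discontinuations are therefore not lost to the trial, although the AE tables remain unbalanced.

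**Replacing the window would create the opposite imbalance.** Last dose plus interval allows up to 28 days on rhEPO against 1 day on daprodustat, and so would favour counting post-stopping events on rhEPO. This stands, and it argues for adding analyses instead of changing the primary definition.

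**Conclusion.** The concern holds for the treatment-emergent AE window. With on-schedule dosing, AEs that end treatment are fully captured on daprodustat but only about 86%, 29%, 14% or 7% of the time on rhEPO given three times weekly, weekly, every 2 weeks or every 4 weeks. The bias runs against daprodustat. It is concentrated in the AE-leading-to-discontinuation and fatal SAE tables and is weaker in the Tier 1, Tier 2 and SAE tables. For those broader tables, a true relative risk of 1 would appear as roughly 1.01 to 1.59, depending on the regimen and on the assumed 10-40% of AE subjects with an event at stopping. The upper end needs every rhEPO subject to be on four-weekly dosing, which the SAP offers only for darbepoetin, the PD comparator.

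For CV endpoints only the tail after stopping is unequal, and only the supportive on-treatment analyses are touched. No multiplicity-controlled test depends on either window: Tier 1 p-values are nominal, and Tier 2 uses a false-discovery-rate adjustment to flag signals.

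**What to change.** Keep the +1 day and +28 day definitions. Before unblinding, pre-specify:

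- (a) A repeat of the Tier 1, Tier 2, SAE, fatal SAE and AE-leading-to-discontinuation comparisons, with the window and person-time ending at the last non-zero dose date plus the dosing interval of that dose.
- (b) The same comparisons on the post-randomization AE state already defined in section 10.4.1.4.
- (c) An interval-based sensitivity version of the supportive while on-treatment MACE analysis.

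The cost is SAP wording, one derived date and extra tables. Exposure records already hold dose dates and frequency (sections 6.2.6 and 10.6.3.6), so no new data are needed. Version (a) gives rhEPO longer ascertainment after stopping, so it must be read alongside (b), which does not depend on the dosing interval. The change affects analysis definitions only.
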